#### **16.2.1 DSMB and CEC Composition**

These two committees will include a Data Safety Monitoring Board (DSMB) and Clinical Events Committee (CEC). Each committee will be composed of at least three or more members (at least two physicians from the fields of cardiology and cardiac surgery) who are not directly involved in the conduct of the trial.

#### **16.2.2 DSMB**

The DSMB will review the study at key points during the conduct.

The first DSMB safety review will take place after the first 10 subjects have been implanted followed by a periodic safety review of study data every six months from the date of the first MVAD Pump implant. Members will be provided data summaries (listings) from the clinical study in a blinded fashion without site or physician identification. Based on the safety data, the DSMB may recommend that the trial be

modified or stopped. No formal statistical rule will be defined for stopping the trial for safety reasons.

The DSMB process (including their ability to stop an ongoing study due to safety concerns) is documented in the study specific DSMB Charter.

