### **Previous Patient Experience**

This trial will involve the first clinical use of the MVAD Pump.

However, many of the design aspects of the MVAD Pump were either derived from, or are improvements based on experiences gained from, the HeartWare HVAD. Some of these include integrated inflow, intrapericardial pump placement via a rigid tightening sewing ring, and a gel impregnated outflow graft. Many of the design, pump control algorithms, and alarm features of the MVAD Pump peripherals are the result of lessons learned from the HVAD controllers, chargers, power adapters and batteries. In addition, there has been clinical experience with an Intraventricular VAD manufactured by another company but the impeller design and suspension differ from the MVAD Pump. Positive in-vitro and in-vivo results with the MVAD pump are a substantial base justifying the conduct of a first clinical use of the MVAD pump in patients with refractory end-stage heart failure.

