#### 9.4.4 Implant

Implants may be performed via a median sternotomy or lateral thoracotomy. In all cases a cardiopulmonary bypass is required. Implant procedures are described in detail in section 15 of the IFU which will be provided to each site at study start.

It is critical that accountability of the device is maintained for research records. Federal regulations require that the lots / ID number of the device and any accompanying surgical instruments, controllers or accessories are appropriately noted and tracked (please also see Section 5.8).

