## 12.5 Analysis Sites

The study will be conducted such that: 1) the same protocol will be used at each study site; 2) site investigators and personnel will receive uniform training; and 3) central data management, and monitoring will be applied with equal rigor at all sites. The diversity of hospital and clinical practice settings will add to the scientific validity and generalizability of the findings. Subjects will be pooled across sites for analysis of study endpoints.

Site effects will be considered for the primary endpoint using site as a blocking variable. Sites with at least 8 subjects will retain their identities. Smaller sites will be ranked in decreasing order of size and cumulatively pooled until pooled sites of no less than 8 are achieved.

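### The DSMB listings carry no site or physician identifier, so the independent board cannot tell from them whether harm is concentrated at one site or team

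*Protocol*

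**What the plan says.** Protocol 16.2.2 describes what the board sees: "Members will be provided data summaries (listings) from the clinical study in a blinded fashion without site or physician identification". On timing, "The first DSMB safety review will take place after the first 10 subjects have been implanted", and later reviews come "every six months from the date of the first MVAD Pump implant". The board may recommend that the trial be modified or stopped, but "No formal statistical rule will be defined for stopping the trial for safety reasons". Procedure is left to a separate document: "The DSMB process (including their ability to stop an ongoing study due to safety concerns) is documented in the study specific DSMB Charter". SAP 7.4 likewise defers to a charter. The charter was not among the documents available.

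The setting is given elsewhere. Protocol 4.1: "This trial will involve the first clinical use of the MVAD Pump". Protocol 9.4.4: "Implants may be performed via a median sternotomy or lateral thoracotomy". Protocol 7.1 plans 60 implants at 5 to 10 sites, with 1 to 10 subjects anticipated at each. SAP 4.3 confirms that all patients receive the pump, and SAP 4.4 marks blinding as not applicable.

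The only site-level analysis (Protocol 12.5, SAP 7.5) uses site as a blocking variable for the primary endpoint. Sites with at least 8 subjects stay separate; for the rest, "Smaller sites will be ranked in decreasing order of size and cumulatively pooled until pooled sites of no less than 8 are achieved". None of the adverse event summaries in SAP 8.8.2 is by site.

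**The concern.** Masking in DSMB reports usually protects a comparison between arms. There is no such comparison here. The only plausible purpose is impartiality towards colleagues at the sites, and an anonymous code would largely preserve that.

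What is lost is attribution. The pump is new to every team. Protocol 11.3 says rehabilitation methods vary by center, and 17.10 leaves exit-site dressing practice to institutional guidelines. With no formal stopping rule, the board relies on judgement from these listings. If three serious events appear, members cannot tell from the listings whether they came from one hospital or three. A problem confined to one site could be diluted in the pooled picture, or read as a failure of the device.

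**Working it through.** **1. The plan's own figures.** The plan states no figure for site clustering. The input borrowed below is the assumed 6-month survival of 85% (Protocol 12.3), so expected mortality is 1 − 0.85 = 15%. The sample size built on it reproduces: with n = 57 and an exact one-sided 95% lower bound above 70%, success needs at least 46 alive (bound 0.7008), giving alpha 0.0486 and power 0.862. This point does not depend on that result.

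**2. Who can see site.** The masking sentence applies to the DSMB listings only. SAEs and USADEs reach the sponsor within 24 hours (Protocol 10.0, 10.3.1.3), as do deaths, with device failures within 72 hours (14.3.1). The Medical Monitor may ask for detail (10.3.1.3). The CRO checks records against source at each site (16.1). No section assigns any of them a review for clustering or a duty to report it to the DSMB. The CEC adjudicates events (16.2.3) with no stated remit on patterns by site. The listed reasons for terminating a site (16.7.2) concern conduct, training and enrolment, although the section opens with a general reasonable-cause clause.

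**3. How many looks fall during implantation.** First implant is planned for Q2 2015 and last implant for Q4 2015 (Protocol 6.2). Six months after any date in Q2 falls in Q4, and the next review would fall in Q2 2016. So the board has the 10-implant look and at most one six-monthly look while implants continue. At the 10-implant look there are on average 10/10 = 1 to 10/5 = 2 subjects per site.

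**4. How pooling can hide a cluster (constructed example).** Take ten sites of 6, with 4 deaths in 6 at one site and 4 in 54 elsewhere.
- Pooled: 8/60 = 13%, unremarkable against 15%.
- By site: 4/6 = 67% against 4/54 = 7%.
- Fisher exact p, given 8 deaths in all: [C(8,4)·C(52,2) + C(8,5)·52 + C(8,6)] / C(60,6) = (92,820 + 2,912 + 28) / 50,063,860 = 0.0019. The site is hand-picked, so multiply by ten sites: about 0.019.
- At a true 15%, P(4 or more deaths in 6) = 0.0059 for a named site. For any of ten it is 1 − (1 − 0.0059)^10 = 5.7%.

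**5. What a code could add (assumed rates).** Take six sites of 10. Five sites (50 subjects) have 15% mortality, one site has mortality m, and all 6-month outcomes are known. The pooled flag fires if X + Y ≥ 15, with X ~ Bin(50, 0.15) and Y ~ Bin(10, m). The coded-site flag fires if Y ≥ 4 or, with Bonferroni over six sites, Y ≥ 6.

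| | Pooled, 15 or more of 60 | Coded, 4 or more of 10 | Coded, 6 or more of 10 |
|---|---|---|---|
| m = 30% | 9% | 35% | 5% |
| m = 45% | 20% | 73% | 26% |
| m = 60% | 36% | 95% | 63% |
| False flag, no clustering | 2.9% | 5.0% per site, 26% over six | 0.14% per site, 0.8% over six |

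The first two flag columns do not have matched error rates. Under the strict rule the code helps modestly at 45%, more at 60%, and does worse than pooling at 30%.

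**The case against.** The strongest reply is that site-specific harm is visible to someone. Step 2 shows that identified reports reach the sponsor and CRO during enrolment. Sponsor specialists support implants (Protocol 14.6.4), the sponsor and investigator must act at once on safety circumstances (14.6.1.3), and suspension must be considered if risk rises (13.2). A reader might infer from 16.2.2 that clustered harm cannot be seen at all while implants continue. The documents do not support that. What remains is that the independent board cannot see it in its own listings, and that no stated rule makes others look for it or tell the board.

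The charter may allow codes or requests for data, and the masking sentence could be read as removing names only. Both are possible. The protocol wording points the other way, which is a reason to align the two.

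The numerical illustrations use complete 6-month outcomes, which would not exist at either look during implantation, and per-site counts would be very small at the 10-implant look. This stands: the figures show the mechanism and do not estimate what the board would have detected.

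Finally, members include cardiology and cardiac surgery physicians (16.2.1), so impartiality is a fair aim, and with few sites a code can sometimes be decoded from enrolment counts. This is a real but small cost.

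**Conclusion.** The point holds in a limited form: the board that can recommend stopping or modifying the trial is given listings from which it cannot attribute events to a site or team. No treatment blinding justifies this, and no other planned step is required to fill the gap. It is an inexpensive safety improvement. It is not a flaw in the primary analysis.

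Its size cannot be derived from the documents. Under the assumed 45% mortality at one site of ten, detection is 20% pooled against 26% to 73% with a code, depending on how many false flags are tolerated.

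Four further inferences go beyond the text:
- Most sites need not lose their identity in the site analysis. That follows for about ten equal sites of 6, but six sites of 10 would all stay separate, and the pooling concerns the primary endpoint only.
- Anticoagulation is not said to vary by center. Protocol 17.11 gives one guideline, individualized by patient.
- Surgical approach is not among the items masked.
- The board is not confined to acting on the device as a whole, since it may recommend modifications.

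SAP 5.2 reports an early stop with fewer than 15 subjects enrolled, so the conclusion concerns the design as planned.

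**What to change.** In Protocol 16.2.2, replace the clause withholding site and physician identification with wording to this effect: names of sites and physicians stay masked; each listing carries an anonymous site code, the order of implant within that site and the surgical technique; an anonymous code for the implanting surgeon is added only if the surgeon is recorded; and the DSMB may ask for the identity behind a code. Put the same terms in the charter, and state there that a cluster under one code prompts enquiry and is not a stopping rule.

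The cost is a short text change in two documents and a few extra columns. Technique is already collected (Protocol 9.1.13), and implant order follows from the implant date. The surgeon is not among the implant data listed there, so that code should not be promised without checking the eCRF. The remaining downside is that a member may infer a site from its enrolment count.

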### **16.2.3 CEC**

The CEC will adjudicate events including device malfunctions dynamically. All unanticipated serious adverse device effects and INTERMACS-defined events will be adjudicated by the CEC using the INTERMACS-specific definition. Each event will be adjudicated by an independent CEC committee (at least 3 reviewers) with the final adjudicated result being a consensus of the committee.

The CEC process is documented in the study specific CEC Charter.

## **16.3 Quality System, Audit and Inspection**

### **16.3.1 Quality system**

HeartWare is responsible for implementing and maintaining quality assurance and quality control systems with written Standard Operating Procedures. HeartWare/the CRO is responsible for ensuring that all parties involved with the trial agree to direct access to all trial-related sites, source data and documents, and reports for the purposes of monitoring and auditing by HeartWare/the CRO, and inspection by domestic and foreign regulatory authorities.

The documentation of the trial should be adequate for reconstruction of the course of events (audit trail).

### **16.3.2 Audit**

An audit is the systematic and independent examination of trial-related activities and documents to determine whether the evaluated trial-related activities were conducted, and the data recorded, analyzed and accurately reported according to the CIP, HeartWare/the CRO s Standard Operating Procedures, GCP and applicable regulatory requirements.

The Investigator will permit an appointed person by the Quality Assurance Unit of HeartWare/the CRO to audit the facilities and documentation at agreed times. Auditors are independent of the clinical trial and its performance.

### 16.3.3 Inspection

Inspection is the act by regulatory authorities of conducting an official review of the documents, facilities, records and other resources that are deemed by the authorities to be related to the clinical trial and that may be located at the trial site, at HeartWare, at the CRO, or at other facilities deemed appropriate by the regulatory authorities. The Investigator is obliged to cooperate with any inspection.

### 16.4 Maintenance of Study Documentation

The Investigator must maintain the following documents throughout the study:

- CIP
- IEC Approvals and Correspondence
- IEC Approved ICF
- Correspondence with HeartWare
- Electronic Signature Authorization Form Device Accountability
- Investigator Agreements
- Curriculum Vitae
- Financial Disclosure Forms
- Telephone Logs
- Screening Logs
- eCRFs
- Monitoring Visit Log
- Laboratory Accreditation and Normal Values
- Site Delegation and Responsibility log
- Source Documents supporting information on eCRFs
- Any other study specific documents

### 16.5 Subject Data Protection

Subjects will be identified on the eCRF by a subject identification number. The investigator will maintain a confidential subject identification list separate from investigational files to link medical records and subject identification numbers.

All information and data sent to HeartWare or their authorized representative, concerning subjects or their participation in this study, will be considered confidential. All data used in analysis and reports will be used without identifiable reference to the subject. At all times throughout the study, confidentiality shall be observed by all parties involved. All data shall be secured against unauthorized access.

All subjects consented for this study will be informed and must agree to the use and disclosure of their study information by the institution and investigators to HeartWare, their agents and representatives, the Competent Authorities (CAs) or other government agencies or review boards.

## 16.6 CIP Modifications

Changes to the CIP during the trial will be documented as amendments. The amended CIP will be signed by the relevant personnel at HeartWare, and by the Investigator(s).

Depending on the contents of the amendment and local legal requirements, the amendment will be submitted to the relevant IECs and, where necessary, to the relevant CAs.

The Investigator should not implement any deviation from, or changes to the CIP, without agreement by HeartWare and the CRO and prior review and documented approval/favorable opinion of the appropriate IEC and, if legally required, CAs, except where necessary to eliminate an immediate hazard to the subjects, or when the change(s) involve only logistical or administrative aspects of the trial.

If an amendment substantially alters the trial design, increases the potential risk to the subjects or affects the treatment of the subject, then the Information Sheet must be revised and submitted to the relevant IEC and, where necessary, to the relevant CAs, for review and approval. When a subject is currently undergoing trial procedures and is affected by the amendment, then the subject must be asked to consent again using the new Information Sheet. The new Information Sheet must be used to obtain consent from new subjects before enrollment.

## 16.7 Compliance/ Investigational Site Termination

### 16.7.1 Compliance

Compliance is the adherence to all trial-related requirements, to Good Clinical Practice (GCP) and to regulatory rules and regulations.

### 16.7.2 Investigational Site Termination

An initiative for center closure or study termination can be taken at any time either by the sponsor or by the investigator, provided there is reasonable cause and sufficient notice is given in advance of the intended termination. HeartWare reserves the right to terminate an investigational site from the study for any of the following reasons:

- Repeated failure to complete case report forms
- Failure to obtain ICF
- Failure to report SAEs and USADs
- Loss of or unaccountable investigational device inventory
- Repeated CIP violations
- Failure of investigator to comply with training or Instructions for Use
- Failure to screen and/or enroll an adequate number of subjects
- Insufficient subject and caregiver/Companion training

## 16.8 Record Retention

HeartWare and all participating Investigators must establish and maintain records and reports. The Investigator must maintain the signed ICFs, eCRFs, study documentation (listed above) and source documents for at least 15 years from the date of the manufacture of the last product in agreement with EU directive 90/385/EEC, Annex 6, section 4, and in agreement with the local regulations. HeartWare should be contacted if the Principal Investigator plans to leave or otherwise absent themselves from the investigational site.

In the event of a CA audit, the Investigator must allow CA access to the study records for inspection and copying. The Investigator must inform HeartWare of any CA audit and provide HeartWare with a copy of any Observations.

The trial master file, the eCRFs, and other material supplied for the performance will be retained by HeartWare according to applicable regulations and laws.

## 16.9 Site Training

Sites will be trained by HeartWare on the device usage and on implant technique as appropriate. Training on GCP, CIP required procedures and data collection will be provided by the vendor(s).

## 16.10 Confidentiality of trial results

The results of this trial are confidential and are not to be transmitted to a third party in any form or fashion. All persons involved in the trial are bound by this confidentiality clause.

## 16.11 Publication policy

The sponsor and the investigators are committed to the publication of the results of this study. The results of the trial will be submitted for publication in an international peer-reviewed heart failure or cardiothoracic surgical journal. Draft manuscripts of publications will be prepared in co-operation between HeartWare and the Coordinating Investigator/Investigator(s). Joint publications are only possible if all parties agree. All editorial decisions will be made jointly by HeartWare and the Coordinating Investigator/Investigator(s).

HeartWare reserves the right to review any publication pertaining to the trial before it is submitted for publication. Neither party has the right to prohibit publication unless publication can be shown to affect possible patent rights or regulatory submission requirements.

In case of discrepancies with other contracts, the provisions of the CIP shall prevail.

**16.12 Final report**

An interim report (after 6 month) and a final report, integrating medical and statistical aspects, will be prepared. This will be authorized by the relevant personnel of HeartWare, and the Coordinating Investigator on behalf of the Investigators. The Investigator(s) will be provided with a copy of the summary of the final report. HeartWare will provide the CA and IEC with the complete clinical trial report within 1 year after the end of the trial or on request, where required.

**16.13 Organization/ Site personnel**

It may be necessary to define additional site personnel (e.g., doctors, nurses, technicians) who have a special responsibility for the performance of portions of the trial at a site under the auspices of the Investigator. The information regarding all site personnel taking part in the trial will be documented and stored in the Investigator s site file.

**17.0 APPENDICES**

**17.1 Time and Event Schedules**

**17.1.1 Screening to Month 24**

Event / Assessment	Screening/ Pre-implant 72 hours before Implant	Day 1-3/ During initial Hospitalization	Discharge	Month 1, 3 +/-7 days	Month 6 + 14 days	Month 12, 18 +/-14 days	Month 24 + 14 days
Informed Consent	X						
Inclusion/Exclusion	X						
Demographics	X						
Cardiovascular/ Medical history & Hospitalization/ INTERMACS Patient Profile	X						
Subject training (HeartWare MVAD and BP Management)			X				
Urine Pregnancy Screen	X						
Safety Laboratory Chemistry and Hematology	X	X 		X	X	X	X
Hemodynamic Parameter/ Vital signs 	X	X		X	X	X	X
IBPM & Diary Assessments 			X	X	X	X	X
Echocardiogram 	X 			X	X	X	X
Implant Data		X 					
MVAD Pump Parameters 		X		X	X	X	X
Log File Download			X	X	X	X	X
Driveline Care Assessment			X	X	X	X	X
NYHA Classification	X			X	X	X	X
6-Minute Walk	X			X	X	X	X
NIH Stroke Scale / Modified Rankin Scale 	X			X	X	X	X
Quality of Life Questionnaire (EuroQol EQ-5D-5L)	X			X	X	X	X
Kansas City Cardiomyopathy Questionnaire (KCCQ)	X			X	X	X	X
Concomitant Medications	X	X	X	X	X	X	X
Adverse Events	X	X	X	X	X	X	X

 Day 3 only     Detailed schedules in Section 9.1.5 of CIP     Echocardiograms obtained within the 6 months prior to ICF may be used for screening  
 Implant=Day 1     MVAD Pump parameters will also be recorded daily post discharge until the patient's blood pressure is stable as defined in Section 9.1.5.2 and at any subsequent hospitalization     In addition obtain MRS and NIHSS at time of stroke and at 12 weeks and 24 weeks post-stroke (+/- 7 days)

**17.1.2 Follow- up after Explant of MVAD® Pump**

Event / Assessment	Explant	Month 1 post explant +/-7 days	Month 6 post explant +/-30 days	Month 12 post explant +/-30 days
Visit Date / Survival Status		X	X	X
Concomitant Medications	X			
Adverse Events	X			

**17.2 New York Heart Association (NYHA) Functional Classification**

The subject's functional status will be assessed by a qualified individual at the institution (who is not associated with the trial) by utilizing the NYHA functional classification below:

**ACC/AHA vs. NYHA Classification of Heart Failure**

ACC/AHA Stage		NYHA Functional Class	
Stage	Description	Class	Description
A	Patients at high risk of developing HF because of the presence of conditions that are strongly associated with the development of HF. Such patients have no identified structural or functional abnormalities of the pericardium, myocardium, or cardiac valves and have never shown signs or symptoms of HF.	No comparable functional class	
B	Patients who have developed structural heart disease that is strongly associated with the development of HF but who have never shown signs or symptoms of HF.	I (Mild)	No limitation of physical activity. Ordinary physical activity does not cause undue fatigue, palpitation, or dyspnea.
C	Patients who have current or prior symptoms of HF associated with underlying structural heart disease.	II (Mild)	Slight limitation of physical activity. Comfortable at rest, but ordinary physical activity results in fatigue, palpitation, or dyspnea.
		III (Moderate)	Marked limitation of physical activity. Comfortable at rest, but less than ordinary activity causes fatigue, palpitation, or dyspnea.
D	Patients with advanced structural heart disease and marked symptoms of HF at rest despite maximal medical therapy and who require specialized interventions.	IV (Severe)	Unable to carry out any physical activity without discomfort. Symptoms of cardiac insufficiency at rest. If any physical activity is undertaken, discomfort is increased.

ACC/AHA = American College of Cardiology/American Heart Association; HF = heart failure; NYHA = New York Heart Association

